### Data analytic plan.

Aim 1: Adapt the FCU Online for low-income parents of school-age children in response to the COVID-19 crisis. Our investigative team will use a formative development process of adaptation to develop new modules and adapt existing content for the FCU Online derived from the FCU Online for middle school ([name] et al, 2019; Danaher et al., 2018) and the FCU Online for young children (currently in development). This version of the FCU Online will address risk factors associated with the COVID-19 crisis, including stress, coping, and learning at home. We will examine the usability and feasibility of the content through focus groups with stakeholders, schools, and parents (N=20).

Aim 2: Conduct a pilot test of the efficacy of the adapted FCU Online. Analyses for Aim 2 will involve two goals, first to examine evidence of feasibility and tolerability of the intervention, and second, to examine evidence that the intervention engaged the putative mechanisms (self regulation, parental depression, and effective parenting skills), and was associated with hypothesized outcomes (youth: depression and conduct problems; parent pandemic related coping). Evidence regarding feasibility and tolerability of the intervention will include descriptive information examining participants' and therapists reports on treatment process, including participant perceptions of the intervention, views regarding the utility of specific treatment components, and data regarding engagement with online materials (e.g. frequency/duration of visits to webpages for FCU-online materials).

Aim 2a and 2b: Main-effects of FCU on mechanisms and outcomes. In line with NIMH's emphasis on experimental therapeutics, a core goal of the proposed project is to demonstrate that the adapted FCU-Online program successfully engages the hypothesized mechanisms of intervention effects (improved self-regulation, improved parenting, and reduced parental depression), as well as hypothesized outcomes. We will examine the main effects of the FCUOnline on mechanisms and outcomes using intent-to-treat analyses, examining all families assigned to the intervention or control group regardless of dosage.

Because the RCT employs a waitlist control condition, with waitlist families offered the intervention following the 4-month assessment, ITT analyses of primary concern focus on possible outcomes at 2-month and 4-month assessments. Time-specific effects of treatment will be examined as regression analyses, predicting time-specific outcomes at wave 2, 3, and 4 by a binary treatment-assignment variable, controlling for baseline levels of the outcome. We will also examine trajectories of change across multiple assessment waves, employing latent growth models, with treatment assignment predicting the rate of change in the outcome over time (e.g. Singer, Willett, & Willett, 2003). We predict significant benefits of the intervention, compared to the control condition, on putative mediators and outcomes at the 2-month and 4-month assessment points. Because the waitlist control group will be offered the FCU-Online following the 4-month assessment, we expect attenuated treatment and control-group differences at the 6-month assessment.

Aim 2c: Examination of mechanisms of FCU effects. Although the main-effects analyses for Aims 2a and 2b represent our core approach to demonstrating our ability to engage both mechanisms and outcomes, we will also formally test mediation of effects on outcomes via the proposed mechanisms. Analyses for Aim 2b will involve tests of mediation, using path modeling approaches that test the statistical significance of the indirect effect of the intervention on targeted outcomes through proximal mediators. Due to the waitlist-control design, we will examine intervention effects on the mediator at 2-months, to the outcomes of interest at 4-months. We will also explore intervention effects on the mediator at 4-months, to the outcomes at 6-months, although the waitlist control condition will be offered the FCU-online between the 4-month and 6-month assessment, which may attenuate treatment and control-group differences at the 6-month assessment. Indirect effects will be tested using Bootstrapped Standard Errors(MacKinnon, Lockwood, Hoffman, West, & Sheets, 2002).

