## Pilot Study (n=180 families)

We will recruit and randomly assign 180 families with school aged children between the ages of 10 and 14 to one of two conditions: (a) FCU intervention (n=90), or (b) a waitlist control group (n=90) that will receive school/ community resources as usual and then offered the intervention immediately after completing the 4-month assessment. This design will enable us to evaluate FCU effects on targeted parent/ youth outcomes. Participation in this study will be 6 months for all families, regardless of condition.

The FCU preventive intervention historically has been delivered in face-to-face sessions between family consultants and parents. Family consultants would do motivational interviewing to determine existing concerns in the family, and motivate parents to make positive change in their parenting and family dynamics. They would provide feedback on the family assessment, and offer coaching and/ or resources to help parents make desired changes. The FCU intervention is intended for prevention, not treatment, of serious youth behavior and to promote growth in positive school and social behaviors. For this project we have developed a computer app that scores family assessments, provides feedback, and provides skill-building content similar to what was previously offered to parents face-to-face. In this project, parents will use this app and receive individualized coaching over the phone or Zoom (depending on parent choice). Throughout this document the word "telehealth" is used to refer to this "app + remote coaching" mode of delivery. The app is not "intended for use in the diagnosis of disease or other conditions, or in the cure, mitigation, treatment, or prevention of disease in man." However, the coach-parent relationship may offer therapeutic benefits.

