Activities"). These tools include videos, animated videos, parenting tips, and interactives. Parents will also be given the opportunity to practice parenting skills. Parents will be able to log-in as often as they like and interact with any of the parenting Skills Sessions on the app. In addition, a Consultant will contact them after completion of the first module to talk through their results, help them set goals, offer support over the phone/ Zoom, and help motivate parents to improve parenting practices. Parents will be able to contact their Consultant as often as they like and will have at least 5 scheduled phone sessions with a consultant (i.e., one after the completion of each module). We anticipate that each of these checkins might take around 20 minutes, but will adapt to the needs of the family. Each of these sessions will be recorded via Zoom, as described above.

Caregivers in both conditions will be invited to participate in follow-up questionnaires at 2 months, 4 months, and 6 months after baseline. This survey will be identical to the baseline assessment so that we can evaluate change over time in the assessed constructs. Parents will once again have options regarding completing the survey on their own or as an interview, via Zoom or phone. Youth data will only be collected at baseline and 6 months after baseline. Youth will also have the option to complete the survey on their own or as an interview over Zoom or phone. The estimated time needed for parents to complete each of these follow-up questionnaires is 45 minutes to an hour; the estimated time needed for youth to complete each follow-up interview is 30 minutes. At the time of the 2-month follow up, parents in the intervention condition will also complete a 2-page FCU Online Satisfaction Survey. This survey will also be completed via Qualtrics.

All families will be compensated for their time. Parents will receive \$75 for completing assessments at baseline, 2 months, 4 months, and 6 months for a total of \$300. Youth with receive \$25 for completing assessments at baseline and 6 months, for a total of \$50.

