#### **Recruiting aids:**

Parents will be compensated for their participation in the research study. Parents will be paid for all *research* assessments (as opposed to the brief 5-minute assessments that are integrated into the app) and can earn up to \$300 for their participation. Intervention and waitlist control families will receive equal compensation. All parents will be asked to complete the *research* assessment 4 times within a year: at baseline, and then follow-up assessments at 2 months, 4 months, and 6 months after baseline. Parents will receive one \$75 check or gift card per household after completing and returning each assessment. Youth will be paid \$25 (via check or gift card) after completing the baseline assessment and again after completing the 6-month follow-up assessment.

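### The 4-month effect on parent-reported outcomes comes from a regression on treatment and baseline alone, so the 2-month scores of families missing month 4 go unused; a joint model of both waves is the better choice.

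*Combined protocol and SAP*

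**What the plan says.** All references are to the combined protocol and SAP.

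- **Time points.** In the Data analytic plan (Aim 2a and 2b), "ITT analyses of primary concern focus on possible outcomes at 2-month and 4-month assessments".
- **Model.** The effects come from regressions run one wave at a time, "predicting time-specific outcomes at wave 2, 3, and 4 by a binary treatment-assignment variable, controlling for baseline levels of the outcome". Treatment and the baseline score are the only predictors named.
- **Additional model.** "We will also examine trajectories of change across multiple assessment waves, employing latent growth models, with treatment assignment predicting the rate of change". The plan does not say which waves enter.
- **Parent data.** Under Pilot Study, "Caregivers in both conditions will be invited to participate in follow-up questionnaires at 2 months, 4 months, and 6 months after baseline", with the same survey each time. A family lost before month 4 will therefore often have a 2-month score.
- **Youth data.** "Youth data will only be collected at baseline and 6 months after baseline". Youth-reported outcomes have no 2- or 4-month score and lie outside this point.
- **Missing data.** The plan names no imputation, full-information likelihood, auxiliary variable or other method.

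**The concern.** With treatment and baseline as the only predictors, a family without a 4-month score drops out of the 4-month regression. What it reported at 2 months, usually the best available guide to its 4-month score, is discarded.

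Two things are at stake. The smaller is precision. The larger is bias: if the families missing at month 4 were selected on 2-month status in one arm and not in the other, or in opposite directions, then those who remain are no longer comparable given baseline alone.

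The design gives some reason to consider this. It is unblinded, and the waitlist arm is "then offered the intervention immediately after completing the 4-month assessment", an incentive to complete month 4 that the FCU arm lacks. A waitlist family doing badly at 2 months may stay in order to get the program, while a similar FCU family may give up. Payment works the other way: "Intervention and waitlist control families will receive equal compensation". The documents do not show that such dropout occurred.

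There is no conflict with the intent-to-treat statement, which concerns how much of the program a family took up.

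**Working it through.** **Inputs.** From the documents: 90 families per arm; parent surveys at baseline, 2 and 4 months; the per-wave model. The documents give no attrition rate, between-wave correlation, SD, effect size, alpha or power, so there is no planned figure to reproduce. Everything else below is assumed. Scores are in SD units and lower is better.

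**Step 1: where the bias comes from.** Let β be the coefficient of the 2-month score in a regression of the 4-month score on baseline and 2-month score:

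β = (r24 − r02·r04) / (1 − r02²)

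With correlations 0.60 (baseline–2), 0.50 (baseline–4) and 0.65 (2–4), β = (0.65 − 0.30)/0.64 = 0.547. If dropout shifts the mean 2-month score (given baseline) of the families still observed by Δ in each arm, then per-wave bias ≈ β(Δ_FCU − Δ_control). Equal shifts cancel. A bias of −0.060 needs a difference in shifts of 0.060/0.547 = 0.11 SD.

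**Step 2: size of the bias.** Simulation with 3,000 trials per cell and true effect −0.30 SD at 2 and 4 months. Dropout at month 4 is logistic in the 2-month score, calibrated to the same rate in each arm. The per-wave regression is compared with a joint maximum-likelihood estimate that uses the 2-month score. First correlation set, 20% missing:

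| Slope on 2-month score, FCU / control | Per-wave bias | Joint bias |
|---|---|---|
| 0 / 0 | +0.001 | +0.001 |
| 1 / 1 | −0.003 | −0.003 |
| 0.5 / 0 | −0.035 | −0.001 |
| 1 / 0 | −0.060 | +0.002 |
| −1 / 0 | +0.063 | +0.001 |
| 1 / −0.5 | −0.092 | +0.005 |

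Negative bias flatters FCU. Across this set and two others (0.65/0.60/0.70 and 0.50/0.40/0.50), at 20% missing:

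- Random, rate-only, baseline-dependent or alike in both arms: at most 0.005 SD.
- FCU arm only: 0.03–0.06 SD, for or against FCU depending on who leaves.
- Opposite directions: 0.06–0.09 SD, with up to 0.097 SD in repeat runs.
- SD of the estimate: 0.13–0.16, so the arm-differential biases are about 0.2–0.65 of it.
- Joint model: at most 0.008 SD throughout.

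The arm-differential range is 0.01–0.05 SD at 10% missing and 0.04–0.14 SD at 30%. With 30% missing in FCU, 10% in control and slopes 1/0, per-wave bias is −0.093 against −0.003 for the joint model. If half the missing families left at random before month 2, per-wave bias falls to 0.02–0.06 SD.

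**Step 3: false positives.** With no true effect and 20% missing, the 5% per-wave test rejects 5.1–7.5% (FCU only) or 7.0–10.0% (opposite directions; up to 10.9% in repeat runs). The joint model rejects 4.4–5.5%.

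**Step 4: precision under random dropout.** With share d missing month 4 and partial correlation ρp between the 2- and 4-month scores given baseline:

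Var(joint)/Var(per-wave) = 1 − d·ρp²

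For correlations 0.6/0.5/0.75, ρp = 0.45/√(0.64 × 0.75) = 0.65. At d = 0.20 the ratio is 1 − 0.20 × 0.422 = 0.916. The 72 observed families per arm then count as 72/0.916 = 78.6. For 0.5/0.5/0.5, ρp = 0.333, the ratio is 0.978 and the effective number is 73.6. Power for an assumed 0.35 SD effect (two-sided 5%) rises from 0.679 to 0.717 and to 0.689 respectively. With no dropout the two methods agree.

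**Step 5: can the growth models stand in?** With the effect at −0.30 at both 2 and 4 months, a linear slope over waves 0/2/4 implies a 4-month effect of −0.30 to −0.33. With month 6 added and its effect halved, it implies −0.11 to −0.14. Much of that shortfall reflects the assumed plateau: with no attenuation at month 6 the slope already implies only about −0.19 to −0.22.

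**Step 6: limit of the remedy.** If dropout depends on the unseen 4-month score, per-wave bias is 0.06–0.23 SD and the joint model leaves 75–87% of it (first set, slopes 1/0: −0.133 against −0.100).

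**The case against.** Baseline-adjusted regression at each wave is a standard, valid estimator and equals the joint model when month 4 is complete. On this view the real gap is an unstated missing-data method, and complete-case analysis is inferred from silence. The growth models in the same paragraph can use the 2-month scores. The waitlist incentive most directly predicts different dropout rates, which do no harm by themselves, and both arms have payment, interview options and reminder calls. The bias is below one standard error, the remedy is partial, and this is a completed pilot.

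Much of this stands. The regression is not wrong in itself, imputation that includes the 2-month score would serve as well as a joint model, and the harmful mechanism is unproven. The opposite-directions case is the extreme of the assumed range.

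It does not remove the point. The model is stated with its predictors, and nothing in the plan brings the 2-month score into it. The growth models target rate of change over unspecified waves, so they are not a stated estimate of the 4-month difference. The joint analysis performs as well or slightly better where there is no bias, so adopting it does not depend on proving the mechanism.

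**Conclusion.** The point holds for parent-reported outcomes at month 4. As written, the analysis discards 2-month scores that bear on a time point of primary concern. It leaves the estimate open to a bias of about 0.03–0.10 SD at 20% missing if dropout follows 2-month status differently by arm, and close to zero otherwise. The variance saving is 1–13% over 10–30% missing. All of these sizes rest on assumed correlations, attrition and dropout mechanisms. This is a worthwhile improvement, not a fatal flaw. The joint model does not protect against dropout driven by the unseen 4-month score.

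**What to change.** - For each parent-reported outcome, estimate the 2- and 4-month effects from one likelihood-based model of both waves: unstructured covariance, treatment-by-time and baseline-by-time terms, all randomised families. Equivalently, keep the 4-month regression but fit it by full-information likelihood or after multiple imputation, with the 2-month score included.
- Keep the per-wave regressions as a sensitivity analysis, and report missingness by arm and wave. That table will show how much this point matters in practice.
- Add a sensitivity analysis for dropout that depends on the unseen score, for example shifting imputed FCU-arm 4-month scores by 0 to 0.5 SD. At 20% missing, 0.5 SD moves the effect by 0.20 × 0.5 = 0.10 SD.
- State which waves enter the growth models.
- Leave the youth-reported 6-month analysis as it is.

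The cost is a little more analysis work and no new data. The 2-month estimate will barely change. The phase table in section C marks the pilot as completed, so the change should be dated, reported as made after data collection, and shown beside the per-wave results originally planned.

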Aim 2b: Evaluate FCU effects on targeted parent/youth outcomes at post-treatment and follow-up, and examine mechanistic pathways via mediation analyses. We will examine FCU effects on core targeted outcomes at post-treatment and follow-up, and will conduct mediation analyses to examine whether hypothesized mediators explain intervention effects on targeted outcomes. We predict that the FCU will predict improved parenting skills, reduced parental depression, and improved self-regulation, which in turn will predict reduced youth depression and problem behavior, as well as improved parent and youth coping with COVID-19.

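### Testing indirect effects with bootstrapped standard errors, read literally, gives up about 1 to 24 points of power at N=180 against a percentile bootstrap interval

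*Combined protocol and SAP*

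**What the plan says.** Mediation is a listed aim. Under Specific Aims, Aim 2b, the team "will conduct mediation analyses to examine whether hypothesized mediators explain intervention effects on targeted outcomes". The Data analytic plan, Aim 2c, describes "path modeling approaches that test the statistical significance of the indirect effect of the intervention on targeted outcomes through proximal mediators". On timing, it states that "we will examine intervention effects on the mediator at 2-months, to the outcomes of interest at 4-months", with a second, exploratory set from 4 to 6 months. The only statement of the test is "Indirect effects will be tested using Bootstrapped Standard Errors", followed by a citation to a methods paper. No section gives an interval type, critical value, alpha, number of resamples, mediation covariates, expected path sizes or power.

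The same section ranks this work below the main comparisons: "Although the main-effects analyses for Aims 2a and 2b represent our core approach".

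**The concern.** A standard error is not in itself a test; a reference distribution is also needed. The usual one is the normal: reject when the estimated product, divided by its bootstrap standard error, exceeds 1.96 in absolute value. Bootstrapping improves the denominator but leaves the normal reference in place. The product of two estimated coefficients is close to normal only when at least one path is large relative to its standard error. At small to moderate paths it is skewed, and a symmetric test rejects too rarely.

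The risk is that a real indirect effect is missed and then read as evidence that the intervention does not work through the proposed mechanism. The opposite error is not at issue, because the literal test does not create false mediation claims. The same bootstrap draws also yield a percentile interval, which does not assume normality.

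**Working it through.** **Inputs from the documents.** N=180, 90 per arm (Pilot Study section); mediator at 2 months, outcome at 4 months; bootstrapped standard errors. The plan states no power figure for mediation, so there is nothing to reproduce.

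**Assumptions.** Two-sided alpha 0.05; paths in roughly SD units, where *a* is intervention to mediator and *b* is mediator to outcome; a range of path sizes; full retention, then 20% loss (180 × 0.8 = 144).

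**Step 1: why the test is conservative.** Write z_a = a/SE_a and z_b = b/SE_b. The large-sample standard error of the product is √(a²·SE_b² + b²·SE_a²), so

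z_ab = z_a·z_b / √(z_a² + z_b²).

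This is always smaller in size than the smaller of z_a and z_b. If the two are equal, each must reach 1.96 × √2 = 2.77 before the product reaches 1.96.

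**Step 2: one cell by hand.** Take a=0.4, b=0.2, mediator residual variance 1, outcome residual variance 1 − 0.2² = 0.96, no baseline covariates.
- SE_a = √(1/90 + 1/90) = 0.149, so z_a = 2.68.
- SE_b = √(0.96/180) = 0.073, so z_b = 2.74.
- z_ab = 2.68 × 2.74 / √(2.68² + 2.74²) = 1.92.

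Both paths typically clear 1.96 with room to spare, while their product typically falls short. The chance that both paths are individually significant is about Φ(0.72) × Φ(0.78) = 0.764 × 0.782 = 0.60. Simulated power in this cell was 34.7% for the bootstrap-SE z test, 36.9% with the large-sample standard error (Sobel test), 59.0% for the percentile interval and 59.9% for requiring both paths to be significant. Bootstrapping the standard error therefore recovers none of the loss.

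**Step 3: simulation with baseline adjustment.** Mediator M = a·T + 0.6·M0 + 0.8e; outcome Y = 0.5·Y0 + b·M + 0.1·T + 0.8e. The mediator model adjusts for T and M0. The outcome model adjusts for M, T and Y0, with or without M0. Each trial used 1,000 case-resampling draws; there were 1,500 trials per power cell (Monte Carlo SE at most 1.3 points). Power at N=180, z test v percentile interval (loss in points):

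| a | b | M0 in outcome model | M0 not in outcome model |
|---|---|---|---|
| 0.3 | 0.20 | 26% v 50% (24) | 41% v 62% (21) |
| 0.4 | 0.20 | 45% v 67% (22) | 63% v 82% (19) |
| 0.4 | 0.25 | 65% v 82% (17) | 79% v 90% (11) |
| 0.5 | 0.25 | 79% v 89% (10) | 93% v 97% (4) |
| 0.5 | 0.30 | 90% v 96% (6) | 97% v 98% (1) |
| 0.5 | 0.40 | 97% v 98% (1) | 98% v 99% (1) |

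At N=144, a=0.4, b=0.25: 45% v 67% with M0 and 61% v 79% without.

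**Step 4: a simpler model.** The Step 2 model was run over a=0.2 to 0.8 and b=0.14 to 0.50, with 1,000 data sets per cell and 500 resamples each. The loss at N=180 ran from 0.1 points (both paths very large) to 24.3 points (a=0.3 or 0.4 with b=0.2). The z test stayed within about 4 points of the Sobel test in every cell.

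**Step 5: cost in type I error.** In the Step 3 model (six null cells for each covariate set, 4,000 trials each), null rejection at N=180 was 0–4.5% for the z test and 0.1–6.3% for the percentile interval. At a=0, b=0.3 it was 2.3–3.3% v 5.4–5.6%; at a=0.6, b=0 it was 3.8% v 6.2–6.3%. The simpler model gave 0.0–4.7% v 0.2–6.5%. A bias-corrected bootstrap interval reached 8.7%, so the type of interval matters.

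**The case against.** **The decision rule is inferred.** The phrase may be loose wording for a bootstrap interval, and the cited methods paper is not available here to settle it. If so, there is no power loss. This stands as a limit. What the documents firmly show is that the rule is missing, and one sentence settles either reading.

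**The loss by path size depends on the model.** At a=0.5, b=0.3 the adjusted model gives 1 to 6 points and the simpler one 79.5% v 89.9%, or 10.4. At a=0.5, b=0.2 the simpler model gives 22.8. This also stands: the overall range is robust, but the figure for a given pair of paths is illustrative.

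**Part of the gain is looser size.** True, but it is the smaller part. In the simpler model, requiring both paths to be significant had null rejection of at most 5.7% at N=180 and power within 2.3 points of the percentile interval in every non-null cell. In a smaller run of the adjusted model (600 trials), a 96% percentile interval had null rejection of 4.2% at a=0.6, b=0. It still reached 46% at a=0.3, b=0.20 and 79% at a=0.4, b=0.25, against 29% and 64% for the z test.

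**Very small paths are missed either way.** At a=0.2, b=0.14, power is 3.6% v 12.6%. The change helps in the middle range only.

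**Several tests are planned.** Three mechanisms and three outcomes give 3 × 3 = 9 pairs, with no multiplicity rule. At the highest null rates in the adjusted model, nine null pairs would give 9 × 0.063 = 0.57 expected false declarations, against 9 × 0.045 = 0.41 for the z test. That is a reason to report the number of pairs tested, not to keep a test that is conservative by accident.

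**This is a secondary analysis in a pilot.** Correct, and it limits the importance of the point.

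**Conclusion.** The concern holds. Taken at its word, the plan tests a skewed product as if it were normal. At N=180 this costs about 1 to 24 points of power against a percentile interval from the same draws. The loss is largest at a of 0.3 to 0.4 with b near 0.20, and negligible when both paths are large. The size rests on the inferred z test, two-sided 0.05, and path sizes and baseline coefficients that the plan does not give.

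The change is worth making but not critical. Mediation is a stated aim, yet the main comparison is untouched and the literal test errs towards missing effects, not inventing them.

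**What to change.** Replace the sentence with: *Indirect effects will be tested with 95% percentile bootstrap confidence intervals (at least 5,000 resamples of families); an indirect effect is declared when the interval excludes zero.* The resample count is a working choice to keep simulation noise in the limits small.

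Also:
- State the covariates of the mediator and outcome models, including whether the baseline mediator enters the outcome model.
- Note that null rejection can slightly exceed 5% (about 6% in simulation) when one path is zero.
- Report how many mediator-outcome pairs were tested.
- Keep bootstrap standard errors as descriptive output if wanted.

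The cost is one sentence and these notes, with the same software and draws and no new data. The phase table in section C lists the pilot as completed, so the change should be dated. If the mediation results have already been seen, both tests should be reported so that the choice cannot be made on the result.
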